## 5.2 Exclusion criteria

- Patients receiving Ilaris treatment for other autoimmune diseases than CAPS

## 6 Exposure and assessments

Ilaris® may be discontinued at any time at the discretion of the treating physician. Discontinuation of treatment with Ilaris® does not imply that the patient must be removed from the Registry. Whenever possible, patients exposed to Ilaris® should continue to be followed for safety-related outcomes (refer to the Schedule of Assessments).

Patients and/or their respective parents/legal representative (if minors) have the right to withdraw from the Registry at any time, without prejudice, and are not obliged to state their reasons for Registry discontinuation. If a patient or parent/legal representative declares his or her wish to discontinue from the Registry, the treating physician will complete the Disposition CRF. Before considering a patient lost to follow-up, the site staff will make all reasonable attempts to contact the patient or the parent/legal representative to ensure that a Registry outcome of interest is not the underlying reason for the non-response of the patient.

### 6.1 Data collection schedule

There are no required visits associated with the Registry. The data collection schedule will accommodate that of the patient's routine clinical care. A recommended data collection schedule is provided below in [Table 6-1](#).

It is expected that in routine clinical care most patients will receive treatment approximately every 8 weeks at their physician's office although it is recognized that variation may occur in the real-world setting. During follow-up, the treating physician or other staff will ideally collect data during routine clinical visits. The timing though will depend on the individual patients' healthcare management and subsequent availability of relevant information. It is recommended to enter data into the Registry every 6 months. However, it is important, during follow-up, that data entry be retrospective to the previous data collection time point in order to capture a complete record of a patient's Ilaris® treatment and outcomes.

**Table 6-1 Recommended data collection schedule**

Period	Baseline	Follow-up (until study end or premature discontinuation)*
Timing	Enrollment	Every 6 months
Informed consent	X	

Novartis  
Amended Protocol Version 02 clean

Confidential

Page 15  
CACZ885D2401

Period	Baseline	Follow-up (until study end or premature discontinuation)*
Timing	Enrollment	Every 6 months
CAPS phenotype	x	
CAPS genotype (NLRP-3 mutation),if available	x	
Non-CAPS medical history	x	
Vital signs (height, weight, blood pressure)	x	x
Ilaris ® dosing/status	x	x
Historical and concomitant medications for auto-inflammatory disease*	x	x
Selected AEs*		x
Other serious AEs and non-serious adverse events*		x
CAPS clinical assessment *	x	x
CAPS-related clinical testing results, if performed	x	x
Selected local laboratory testing	x	x
Sexual development status (paediatric only)	x	x
Neurocognitive status (paediatric only)	x	x
Cerebrospinal fluid analysis	x	x
Vaccination record and outcome	x	x
Pregnancy status (females of child-bearing potential only)		x
Registry disposition		x

\* These assessments may also be conducted during follow-up for patients who discontinue Ilaris® but remain in the Registry

## 6.2 Patient demographics/other baseline characteristics

It is recommended that the following data elements be collected at baseline:

- Informed consent/paediatric assent
- Demographics, including date of birth, race (where permitted by local regulations)
- Vital signs (current height and weight, blood pressure)
- Indication for treatment with Ilaris®
  - NLRP-3 mutation (if available)
  - CAPS: date of symptom onset and subtype
  - Treatment history
- Clinical assessment of autoinflammatory disease activity (e.g., physician's global assessment, presence and intensity of fever, rash, myalgia, arthralgia, conjunctivitis, headaches)
- Overall results of recent CAPS-related clinical testing, if performed (audiogram, ophthalmologic exam, brain MRI)

- Non-CAPS medical history (by medical record, recent physical exam or diagnostic testing), including:
  1. Auditory (sensorineural hearing loss)
  2. Cardiovascular history and risk factors (i.e., hyperlipidemia, hypertension)
  3. Ophthalmic (nystagmus, uveitis, papillitis/papilledema)
  4. Neurologic (chronic meningitis, headaches, vertigo)
  5. Immune, including severe and/or recurrent infections, immunization history and rheumatoid arthritis or other autoimmune disease
  6. Haematologic (anemia or neutropenia)
  7. Malignancy
  8. Other relevant history
- Ilaris® dosing (date of administration and dose)
- Selected laboratory test results, if performed [serum amyloid A (SAA), c-reactive protein (CRP), erythrocyte sedimentation rate (ESR); any abnormal and clinically significant selected haematology, creatinine, lipids, liver function tests, urinalysis (proteinuria), anti-nuclear antibodies (ANA) and ds-DNA values]
- Cerebrospinal fluid analysis results (if evaluated)
- Paediatric patients age 6 to  $\leq 17$  years only: sexual development status (if evaluated), neurocognitive development status (if evaluated),

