#### 3.2 Secondary objectives

The secondary objectives of the  $\beta$ -CONFIDENT Registry are to:

- Describe the long-term impact of Ilaris® on disease progression (including systemic AA amyloidosis as evidenced by renal function, neurologic and ophthalmologic symptoms, and sensorineural deafness);
- Explore growth and development patterns in children aged  $\geq 2$  or  $\geq 4$  (depending on local label) to  $\leq 17$  years of age exposed to Ilaris®;
- Identify previously unrecognized serious adverse drug reactions in the treated population;
- Describe the usage and patterns of dosing of Ilaris® in routine clinical practice.

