### 6.3 Clinical outcomes

The following data elements will be collected as part of clinical follow-up:

- Date of assessment
  - Treatment status: discontinuation, interruption or changes in Ilaris® dosing and reason for discontinuation, interruption or change
  - Vital signs [current height (paediatric patients only) and weight, blood pressure]
  - Changes in concomitant medications related to auto-inflammatory disease
  - Changes in medical status, including disease progression:
    - AA amyloidosis and renal dysfunction
    - Hearing and vision loss
    - Blindness/vision loss
  - Clinical assessment of autoinflammatory disease activity (symptom presence/intensity)
  - Overall results of CAPS-related clinical testing, if performed (audiogram, ophthalmology, brain MRI)
  - Selected laboratory test results, if performed [SAA, CRP, ESR, creatinine, lipids, liver function tests, urinalysis (proteinuria), ANA and ds-DNA values]
  - Cerebrospinal fluid analysis (if collected)
  - Paediatric patients age 6 to  $\leq 17$  years only: sexual development status (if evaluated), neurocognitive development status (if evaluated),
- 

- Adverse events and serious adverse reactions (refer to [Section 6.5](#))
- Vaccination record and outcome: including vaccinations within 3 months of baseline and throughout follow-up
- Pregnancy status (female patients of child-bearing potential only)

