#### 6.5 Safety

Any patient who receives at least one dose of Ilaris® will be included in the evaluation for safety. Data regarding the occurrence of the following selected adverse events will be specifically solicited:

- Serious infections

*Serious infections are defined as any infections that meet serious criteria (refer to [Section 7.1](#)).*

- Malignancies
- Hypersensitivity reactions to Ilaris®
- Development of autoantibodies (ANA, ds-DNA)
- Clinical manifestations of an autoimmune disease (e.g., lupus, vasculitis, rheumatoid arthritis)
- Vertigo
- Any other Serious Adverse Events (SAEs) (refer to [Section 7.1](#))

Reports of any other adverse events (AEs) potentially related to Ilaris® therapy that are reported during follow-up will also be collected.

In addition, ALL non-serious adverse events which have been reported since 02-Jul-2012 will also be collected during follow-up.

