### 7.1 Adverse events

An AE is the appearance or worsening of any undesirable sign, symptom, or medical condition occurring after starting Ilaris® even if the event is not considered to be related to Ilaris®. Medical conditions/diseases present before starting Ilaris® are only considered AEs if they worsen after starting Ilaris®. Abnormal laboratory values or test results constitute AEs only if they induce clinical signs or symptoms, are considered clinically significant, or require therapy. All selected events (serious infections, malignancies, hypersensitivity reactions and vertigo) and ALL non-serious AEs (if reported after 02-Jul-2012) and serious AEs are to be recorded regardless of whether considered related to Ilaris®.

All AEs recorded on the Adverse Events CRF should include the following information:

- The severity grade (mild, moderate, severe)
- Relationship to Ilaris® (suspected/not suspected)
- Duration (start and end dates or if continuing at Registry discontinuation)
- Whether it constitutes a serious adverse event (SAE)

Any treatment of any adverse event should be recorded on the Adverse Event CRF. Some examples of treatment to be recorded are: no action taken (i.e., further observation only); drug of interest dosage adjusted/temporarily interrupted; drug of interest permanently discontinued due to this adverse event; treatment medication adjusted; non-drug therapy given; patient hospitalized/patient's hospitalization prolonged.

Information on all AEs is included in the individual patient eCRFs which must be updated and committed in the study database on a periodic basis but not later than once a month.

An SAE is defined as an event which:

- Is fatal
- Is life-threatening as it occurred
- Results in persistent or significant disability/incapacity
- Constitutes a congenital anomaly/birth defect
- Requires inpatient hospitalization or prolongation of existing hospitalization
- Is medically significant, i.e., defined as an event that jeopardizes the patient or may require medical or surgical intervention to prevent one of the outcomes listed above
- Transmission of infectious agent via medicinal product

Information about adverse reactions observed in relation to Ilaris® can be found in the local product labeling.

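### Section 6.2 filters the baseline laboratory results that section 6.3 collects unfiltered, so a blank baseline cannot show whether a later positive autoantibody test or renal decline is new

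*Protocol*

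**What the plan says.** Section 6.2 introduces its list with "It is recommended that the following data elements be collected at baseline". The laboratory item, which applies where tests were performed, has two parts. SAA, CRP and ESR come first, without restriction. After a semicolon the request narrows to "any abnormal and clinically significant selected haematology, creatinine, lipids, liver function tests, urinalysis (proteinuria), anti-nuclear antibodies (ANA) and ds-DNA values".

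Section 6.3 lists the follow-up results, again where performed, as "SAA, CRP, ESR, creatinine, lipids, liver function tests, urinalysis (proteinuria), ANA and ds-DNA values". Haematology is gone and there is no restriction to abnormal or significant values. Table 6-1 has a single row, "Selected local laboratory testing", marked at baseline and at follow-up with no qualifier.

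Two stated aims depend on these data. Section 6.5 solicits "Development of autoantibodies (ANA, ds-DNA" as a selected event, and section 9.3 puts other selected events in the primary analysis as proportions or rates with 95% confidence intervals. Section 3.2 sets out to describe disease progression, "including systemic AA amyloidosis as evidenced by renal function".

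**The concern.** To say that an autoantibody has developed, one needs patients known to be negative at the start. To say that renal function has declined, one needs a starting value. Followed as written, section 6.2 asks for neither a negative ANA or ds-DNA result nor a normal creatinine or proteinuria result. It also omits the patients who matter most for misclassification: those already positive at baseline whose physician thought the result unimportant. At follow-up the same patient's result is requested without that screen.

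The gap is one of collection. An analysis plan can define denominators and rules for missing data, but it cannot recover a result that the form never requested. At stake are how a solicited safety event is interpreted and how well a secondary objective can be read.

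**Working it through.** The protocol states no figure on this point, so there is none to reproduce. The check is a comparison of text, followed by an illustration with assumed inputs.

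**Step 1: the three places side by side**

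- Section 6.2, baseline: creatinine, proteinuria, ANA, ds-DNA, lipids, liver tests and haematology, only if abnormal and clinically significant.
- Section 6.3, follow-up: the same tests without haematology, any performed result.
- Table 6-1: laboratory testing at both times, no restriction.

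The qualifier could grammatically attach to haematology alone, but it more naturally governs the whole series after the semicolon. If the narrow sense was meant, the wording still needs correcting, because sites cannot tell.

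**Step 2: what a blank baseline means**

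Under section 6.2 a blank is consistent with three states: tested and normal or negative; tested and abnormal but judged not significant; not tested. The recorded laboratory data do not separate them.

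**Step 3: consequence for each aim**

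- Autoantibodies: a site that follows section 6.2 enters no negative result, so the set of patients with a documented negative baseline is empty. A follow-up positive after a blank may be new or old.
- Renal function: worsening can be measured from a recorded abnormal baseline. Decline from a normal start has no recorded starting value.

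**Step 4: possible size (illustration only)**

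N = 260 is the expected enrolment in the synopsis and section 4. Two inputs are assumptions that the protocol does not give:

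- p: share of patients positive at baseline but left blank as not significant, 5% to 20%.
- i: true new positivity among the rest, 2% to 10%.

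It is further assumed that all patients are tested at follow-up, that old positives remain positive, that blanks are read as negative, and that no physician judgement corrects them. Then:

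- old positives that look new = N × p
- truly new positives = N × (1 − p) × i
- share of apparent new positives that are old = p / (p + (1 − p) × i)

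For p = 5% and i = 2%: 260 × 0.05 = 13; 260 × 0.95 × 0.02 = 4.9; 13 / 17.9 = 72.5%.

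| p | Old positives | Share, i = 2% | Share, i = 5% | Share, i = 10% |
|---|---|---|---|---|
| 5% | 13 | 72.5% | 51.3% | 34.5% |
| 10% | 26 | 84.7% | 69.0% | 52.6% |
| 20% | 52 | 92.6% | 83.3% | 71.4% |

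These are upper limits for each pair of inputs, because testing is optional and physicians will identify some old positives from the chart. With all performed baseline results recorded, p would be known among tested patients, the misclassified share among them would fall to zero, and untested patients could be identified as such.

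**The case against.** The strongest reply is that the laboratory fields are not the only evidence. Clinically significant baseline abnormalities are recorded. The medical history in section 6.2 may draw on diagnostic testing, includes autoimmune disease and has a category for other relevant history. Section 7.1 counts a pre-existing condition as an adverse event only if it worsens after Ilaris is started. Section 6.3 asks for changes in medical status and names AA amyloidosis and renal dysfunction. This stands: it would be too strong to infer that new and old findings can never be told apart. The gap concerns patients with a blank baseline, and for them the separation rests on a physician's judgement whose laboratory basis is not recorded.

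The section 6.2 list is also only a recommendation, and Table 6-1 carries no filter. That lowers the severity, but it leaves sites with conflicting instructions.

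Three further inferences are tempting and not supported:

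- **Seroconversion is lost as an adverse event.** Section 7.1 says "Abnormal laboratory values or test results constitute AEs only if they induce clinical signs or symptoms", or if clinically significant or treated, and its parenthetical list of selected events omits autoantibodies and autoimmune manifestations. But the opening of section 7 has all selected events from section 6.5 recorded in the CRF, and section 6.3 keeps follow-up ANA and ds-DNA results whether or not they are adverse events. What remains is a wording mismatch.
- **Regression to the mean will mimic renal improvement.** This presupposes a change-from-baseline analysis in patients with abnormal baselines. The protocol plans none; section 9.3 speaks of the frequency of progression markers.
- **Event rates will use the total Registry population.** That phrase in section 9.1 concerns categorical baseline variables. Section 9.3 leaves time at risk to the analysis plan.

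**Conclusion.** The point holds in a limited form. Section 6.2 conflicts with section 6.3 and Table 6-1 on which laboratory results to record. Followed literally, it leaves out the normal, negative and not-significant baseline results needed to interpret a solicited safety event and a secondary objective. For patients with a blank baseline, the laboratory data cannot establish newness of an autoantibody or decline from normal renal function.

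How many patients this affects cannot be derived from the protocol. The 13 to 52 patients in the illustration rest wholly on an assumed 5% to 20% prevalence of unrecorded positives, full retesting, and no correction from the chart. Because physician-judged routes exist and the list is advisory, this is a should-fix. It should be settled while charts can still be consulted, since the values cannot be recovered once data collection has closed.

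**What to change.** - **Section 6.2:** delete the qualifier limiting the second group of tests to abnormal and clinically significant values. Ask for every performed baseline result, including normal and negative ones, or an entry of not done, in line with section 6.3 and Table 6-1.
- **Timing:** record each baseline test date relative to the first Ilaris dose. Section 5.1 enrols patients already receiving Ilaris, so a baseline value need not be pre-treatment.
- **Counting rule:** count new autoantibody positivity only among patients with a documented negative baseline and at least one follow-up test, and report how many lack a baseline.
- **Wording only:** make the parenthetical list of selected events in section 7.1 match section 6.5.

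The cost is some eCRF fields, back-entry from charts for patients already enrolled, and smaller denominators. No new test is required. The cure is partial: tests are still recorded only if performed, and some baselines will be on treatment.

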### 6.3 Clinical outcomes

The following data elements will be collected as part of clinical follow-up:

- Date of assessment
  - Treatment status: discontinuation, interruption or changes in Ilaris® dosing and reason for discontinuation, interruption or change
  - Vital signs [current height (paediatric patients only) and weight, blood pressure]
  - Changes in concomitant medications related to auto-inflammatory disease
  - Changes in medical status, including disease progression:
    - AA amyloidosis and renal dysfunction
    - Hearing and vision loss
    - Blindness/vision loss
  - Clinical assessment of autoinflammatory disease activity (symptom presence/intensity)
  - Overall results of CAPS-related clinical testing, if performed (audiogram, ophthalmology, brain MRI)
  - Selected laboratory test results, if performed [SAA, CRP, ESR, creatinine, lipids, liver function tests, urinalysis (proteinuria), ANA and ds-DNA values]
  - Cerebrospinal fluid analysis (if collected)
  - Paediatric patients age 6 to  $\leq 17$  years only: sexual development status (if evaluated), neurocognitive development status (if evaluated),
- 

- Adverse events and serious adverse reactions (refer to [Section 6.5](#))
- Vaccination record and outcome: including vaccinations within 3 months of baseline and throughout follow-up
- Pregnancy status (female patients of child-bearing potential only)

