#### 6.6 Effectiveness/Disease Progression

Information regarding the following aspects of long-term effectiveness (disease progression) will be collected:

- Amyloid A (AA) amyloidosis
- Renal dysfunction
- Sensoneural deafness
- Blindness/vision loss
- Neurologic symptoms
- Growth and development (for children)

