## 9.3 Analysis of registry objectives

Descriptive statistics will be used to summarize all safety and effectiveness criteria. No formal hypothesis testing or statistical significance testing is planned. This approach follows the Guidelines for Good Pharmacoepidemiology Practices, Section D, point 10.

The primary analyses will include evaluating the frequency (proportions or rates and 95% CI) of serious infections, malignancies, hypersensitivity reactions and other selected events. Time at risk (in person-years) for select safety outcomes, such as serious infections and malignancies, where possible, will correspond to the induction period associated with the event (if known) and the temporal relationship to treatment with Ilaris, and will be further described in the SAP.

Additional analyses will explore the frequency of markers of disease progression, such as systemic AA amyloidosis, neurologic and ophthalmologic symptoms, and sensorineural deafness, patterns of paediatric growth and development and the frequency of other SAEs considered potentially related to Ilaris®.

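### The follow-up progression list in section 6.3 joins hearing with vision, repeats vision loss and omits the neurologic item that 3.2, 6.6 and 9.3 treat as a separate marker

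*Protocol*

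**What the plan says.** Objective 3.2 is to describe the long-term impact of treatment on disease progression, and it names systemic amyloidosis (through renal function), "neurologic and ophthalmologic symptoms, and sensorineural deafness". Section 9.3 carries this into the analysis: "Additional analyses will explore the frequency of markers of disease progression, such as systemic AA amyloidosis, neurologic and ophthalmologic symptoms, and sensorineural deafness".

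Section 6.6 says information will be collected on amyloidosis, renal dysfunction, sensorineural deafness, vision loss, "Neurologic symptoms" and, for children, growth and development. Each is its own item.

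Section 6.3 gives the data elements for follow-up. Under "Changes in medical status, including disease progression" it has three lines: amyloidosis together with renal dysfunction, "Hearing and vision loss", and "Blindness/vision loss". Further down it takes "Overall results of CAPS-related clinical testing, if performed (audiogram, ophthalmology, brain MRI".

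**The concern.** The planned output for this secondary objective is a set of frequencies, one per marker. A frequency for deafness needs an entry that means deafness, and a frequency for neurologic progression needs somewhere to record it. Read literally, the list in 6.3 gives neither. A positive entry on the joint line does not say which organ changed, the same vision loss can be entered on two lines, and neurologic change has no line.

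Patients already affected at enrolment raise a second issue. Section 1 describes progressive deafness in many patients with Muckle-Wells syndrome, and sensory organ dysfunction in NOMID. For such a patient the question at follow-up is whether hearing is stable, better or worse. An overall audiogram result with no reference to the previous test may be abnormal in all three cases.

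An analysis plan cannot repair this later. It can define how entries are counted, but it cannot recover which organ a combined entry meant.

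**Working it through.** No arithmetic on rates applies: the protocol gives no event rates, sample size calculation or hypothesis for this objective. The check is a comparison of sections.

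**Step 1. Set the 6.6 organ outcomes against the 6.3 progression lines.** Growth and development is left out because 6.3 covers it elsewhere.

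| Outcome in 6.6 | Line in the 6.3 progression list |
|---|---|
| AA amyloidosis | shared with renal dysfunction |
| Renal dysfunction | shared with amyloidosis |
| Sensorineural deafness | shared with vision loss |
| Vision loss | own line, and again on the hearing line |
| Neurologic symptoms | none |

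Count: 1 with its own line + 3 only on a shared line + 1 with none = 5. The amyloidosis and renal pairing matters least. Objective 3.2 itself reads amyloidosis through renal function, and 6.3 also collects creatinine and proteinuria if performed.

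**Step 2. Look for another source for hearing.** The audiogram is named separately from the ophthalmology result, so the organs are separable there, but only when the test was done and only as an overall result. At baseline, 6.2 gives sensorineural hearing loss its own history item. Table 6-1 marks that history for baseline only, so no follow-up item mirrors it.

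**Step 3. Look for another source for neurologic change.**
- Symptom assessment (6.3): the only neurologic example in the matching baseline item in 6.2 is headache.
- Brain MRI and cerebrospinal fluid: recorded only if done, and neither is a symptom.
- Neurocognitive status: ages 6 to 17 and only if evaluated, so not adults already enrolled or children under 6.
- Vertigo: solicited in all patients under 6.5, as an adverse event.
- Baseline neurologic history (6.2), including chronic meningitis: baseline only in Table 6-1.

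**Step 4. Look at adverse event reporting.** Section 7.1 counts worsening of an existing condition as an adverse event, so new or worse deafness or meningitis can be reported with severity and dates. Serious events and the selected events are recorded regardless of causality. All non-serious events are covered only if reported since 02-Jul-2012, whereas the first patient enrolled in Nov-2009. For those first 31 to 32 months, the only other non-serious events that 6.5 collects are those potentially related to treatment.

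**Step 5. Check which section is the outlier.** The synopsis paragraph on clinical assessments also separates deafness from vision loss, although it too has no neurologic item. On hearing, 6.3 stands alone against the synopsis, 3.2, 6.6 and 9.3. On neurologic symptoms, 6.3 and that synopsis paragraph differ from 3.2, 6.6 and 9.3.

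**The case against.** A reader might infer that deafness and neurologic progression cannot be measured in this registry. The documents do not support that. Section 6.6 commits to collecting each outcome. The lead-in in 6.3 asks for changes in medical status and is open-ended, so worse hearing in a patient already deaf at baseline is reportable there. The audiogram, ophthalmology and MRI results are named individually, vertigo is solicited in everyone, and worsening of any condition is an adverse event. It also does not follow that progression can be shown only in organs that were normal at baseline.

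The eCRF and its completion guidelines are not shown. A line in a protocol list is not necessarily one tick-box, and an overall result need not mean only normal or abnormal. The second vision line may be a drafting slip for a separate hearing item.

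A reader might also want to say what share of patients is affected at baseline, or to require hearing thresholds per ear and visual acuity per eye. The protocol gives no figure for the former. The latter would serve a graded analysis, whereas 9.3 plans descriptive frequencies from routine care.

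All of this stands, and it limits the point. It does not remove the contradiction: 6.6 names topics, 6.3 is the follow-up list of data elements, and the two disagree. The other routes depend on a test having been done or on an event having been reported; they are not a structured assessment of progression.

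**Conclusion.** The point holds as an internal contradiction in the data-collection list for a named secondary objective. Four of the five organ outcomes in 6.6 lack a line of their own in 6.3. The two that matter most are hearing, which cannot be told apart from vision on its line, and neurologic symptoms, which have no line.

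The consequence is conditional on the eCRF following 6.3 literally. In that case:

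- a combined entry can be attributed to hearing only through an audiogram, if performed, or an adverse event report;
- neurologic change is captured only indirectly, through the symptom assessment, brain MRI, cerebrospinal fluid, paediatric neurocognitive status, vertigo and other adverse events;
- an overall test result need not show whether an organ already affected at baseline is stable or worse.

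The number of patients affected cannot be derived from the protocol. The primary safety objective does not rest on this list.

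**What to change.** Align 6.3 with 6.6. Replace the three progression lines with five, each appearing once: AA amyloidosis, renal dysfunction, sensorineural hearing loss, vision loss or blindness, and neurologic symptoms. Rate each as new, worse, unchanged or improved since the last entry. Make the same correction to the synopsis paragraph on clinical assessments, which lacks the neurologic item.

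For audiograms, ophthalmology examinations and brain MRI already performed in routine care, add the test date and the reader's conclusion against the previous test. Numerical values per ear or per eye need not be mandatory.

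The cost is a small eCRF revision and slightly more data entry at each follow-up time point. It requires no new tests or visits, so the study stays observational. Follow-up runs until one year after the last patient is recruited, so the change would still improve the data yet to be collected.
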